## **Appendix 4. HRCT Criteria and Histopathological Criteria for UIP Pattern\***

### **HRCT Criteria for UIP Pattern**

#### UIP Pattern (All Four Features)

- Subpleural, basal predominance
- Reticular abnormality
- Honeycombing with or without traction bronchiectasis
- Absence of features listed (below) as Inconsistent with UIP Pattern

#### Possible UIP Pattern (All Three Features)

- Subpleural, basal predominance
- Reticular abnormality
- Absence of features listed (below) as Inconsistent with UIP Pattern

#### Inconsistent with UIP Pattern (Any of the Seven Features)

- Upper or mid-lung predominance
- Peribronchovascular predominance
- Extensive ground glass abnormality (extent > reticular abnormality)
- Profuse micronodules (bilateral, predominately upper lobes)
- Discrete cysts (multiple, bilateral away from areas of honeycombing)
- Diffuse mosaic attenuation/air trapping (bilateral, in three or more lobes)
- Consolidation in bronchopulmonary segment(s)/lobe(s)

### **Histopathological Criteria for UIP Pattern**

#### UIP Pattern (All Four Criteria)

- Evidence of marked fibrosis/architectural distortion, ± honeycombing in a predominantly subpleural/paraseptal distribution
- Presence of patchy involvement of lung parenchyma by fibrosis
- Presence of fibroblast foci
- Absence of features against a diagnosis of UIP suggesting an alternate diagnosis (hyaline membranes, organizing pneumonia, granulomas, marked interstitial inflammatory cell infiltrate away from honeycombing, predominant airway centered changes, other features suggestive of an alternate diagnosis)

\*Raghu, 2011

**Appendix 5. Radiation Risk Assessment**

The estimated radiation dose that results from participation in this study is based on an estimate is for a “standard patient” such as the MIRD phantom used in the ImPACT dose calculator spreadsheet. However, the ImPACT spreadsheet does not have a model for all CT platforms and for these the DLP\*k method is used. For this method we assume a “standard sized” patient model, scan length is 25 cm (the length of the lungs for the MIRD Phantom) and a k factor of 0.014 mSv/mGy\*cm for a thoracic scan (AAPM report 96 and European Guidelines 2000). For this study the expected doses are summarized in the table below.

Please NOTE that for each visit, one CT exam will be performed. That exam will consist of a required TLC scan. RV scans are not required for the quantitative image analysis data being collected for this study. Effective dose estimates provided: (For this study, visits occur at Baseline, 6 months, 1 year, 18 months and 2 years (i.e. 5 studies).

Summary	
TLC scan - CTDIvol	6.1 mGy
TLC scan – DLP (25 cm scan)	153 mGy*cm
TLC scan only - DLP	153 mGy*cm
Effective Dose per CT exam (TLC only)	2.14 mSv per exam
Effective Dose per year (TLC only) (assume 2 studies each calendar year)	4.28 mSv per year
Effective Dose over entire study (TLC only) (5 studies)	10.7 mSv over entire study

**Average background radiation (excluding medical exposure to population):**

For a comparison, the average annual exposure from background radiation:

Based on National Average:	
United States	3.0 mSv per year
Canada	1.8 mSv per year
United Kingdom	2.5 mSv per year
Australia	2.0 mSv per year
Germany	2.0 mSv per year
India	2-2.5 mSv per year

1 INTRODUCTION

The planned analyses for the Randomized Treatment Period are documented in Part 1 of the Statistical Analysis Plan (SAP) for study FGCL-3019-067: A Phase 2, Randomized, Double-Blind, Placebo-Controlled Study to Evaluate the Safety and Efficacy of FG 3019 in Patients with Idiopathic Pulmonary Fibrosis. This is the part 2 of the SAP, which documents the planned analyses for the Extended Treatment Period. This document is based on the protocol Amendment 5.0 dated 12DEC2016.

In this document, only new definitions and rules will be described; the same definitions and rules described in the Part 1 of the SAP will not be repeated.

2 STUDY DESIGN (EXTENDED TREATMENT PERIOD)

2.1 Enrollment to Extended Treatment

Subjects Enrolled under the Original Protocol and Randomized to FG-3019

All subjects in Arm A whose FVC percent predicted value shows less than 3% absolute decrease from baseline in the Randomized Treatment Period will be offered participation in an Extended Treatment Period. These subjects may continue treatment until FVC percent predicted decreases 3% or more on two consecutive scheduled evaluations compared to the original pre-treatment baseline.

Subjects Enrolled Under Protocol Amendments and Randomized to FG-3019

All subjects in Arm A whose FVC percent predicted value is greater than the original pre-treatment baseline in the Randomized Treatment Period will be offered participation in an Extended Treatment Period and may continue treatment until FVC percent predicted is equal to or less than the pre-treatment baseline on two consecutive scheduled evaluations.

Subjects Randomized to Placebo

All subjects randomized to Placebo (Arm B) will be offered participation in the Extended Treatment Phase for 45 weeks. Placebo subjects in the extension study are treated identically to subjects randomized to FG-3019 in Amendment 1, except for the fact that the baseline for these patients is the time at which they are enrolled into the extension phase (Baseline for Placebo subjects is Week 48 value). Change in FVC percent predicted during the extended treatment phase will be compared to this new baseline. Those subjects whose FVC percent predicted value is either equal to or greater than the new baseline may continue treatment with FG-3019 until FVC percent predicted is equal to or less than the baseline on two consecutive scheduled evaluations.

Subjects in Substudy

Subjects in substudy are not eligible to enroll into the extended treatment.

2.2 Assessments in Extended Treatment Period

- FVC and FEV1 are assessed at 12-week intervals.
- HRCT scan of the chest is performed at 24-week interval during extension period.
- SGRQ questionnaire is administered at 12-week intervals.
- Electrocardiogram (ECG) is assessed at 24-week intervals.
- Laboratory samples for safety assessments are collected at 6-week intervals.
- Serum and plasma samples for biomarker tests (including CTGF) are collected at 24-week intervals.
- Plasma samples for assessing HAHA are collected prior to dosing on Day 1 of Extension Period and at the End of Study (EOS) safety follow-up.
- Adverse events, concomitant medications, procedures, non-drug therapies, oxygen use are collected from signing ICF through End of Study (EOS).

- Vital signs are measured at every clinical visit. On dosing days, vital signs are measured at pre-, intra-, and post-infusion.
- Physical examination is performed at 6-week intervals.

3 STUDY ENDPOINTS AND DEFINITIONS (EXTENDED TREATMENT PERIOD)

3.1 Study Endpoints

- Change from baseline in FVC (L) and FVC (% predicted) at each assessed time point
- Change from baseline in fibrosis score by quantitative HRCT at each assessed time point
- Change from baseline in HRQoL at each assessed time point.

3.2 Definitions of Endpoints in Extended Treatment Period

3.2.1 Efficacy Endpoints

For subjects who were originally randomized to FG-3019, efficacy endpoints are defined as change from the original baseline at study entry. These summaries will enable evaluation of long-term effect.

For subjects who were originally randomized to placebo and rolled over to active in extension, efficacy endpoints are defined as change from baseline as defined as the final assessment during the Randomized Treatment Period. These summaries will enable separate evaluation of effect of active treatment from placebo.

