##### 4.2.3.1 Subjects Enrolled under the Original Protocol and Assigned to Arm A: FG-3019

All subjects in Arm A whose FVC percent predicted value shows less than 3% absolute decrease from baseline in the Randomized Treatment Period will be offered participation in an Extended Treatment Period. These subjects may continue treatment until FVC percent predicted decreases 3% or more on two consecutive scheduled evaluations compared to the original pre-treatment baseline.

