#### **4.2.3.2 Subjects Enrolled Under Amendment 1 or Subsequent Amendments and Assigned to Arm A: FG-3019**

All subjects in Arm A whose FVC percent predicted value is greater than the original pre-treatment baseline in the Randomized Treatment Period will be offered participation in an Extended Treatment Period and may continue treatment until FVC percent predicted is equal to or less than the pre-treatment baseline on two consecutive scheduled evaluations.

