4.2 Handling Dropouts and Missing Data

Missing values in the efficacy and safety parameters will not be imputed. All efficacy and safety will be summarized based on available observed data. Imputation will only be performed on missing or incomplete AE onset date or CM start/stop date. The same imputation algorithm described in SAP Part 1 will be used.

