4.3 Definition of Baseline

For subjects who were randomized to FG-3019 arm, the original baseline defined in the Randomized Treatment Period as described in SAP Part 1 will be used. This definition will enable evaluation of long term treatment effect in safety and efficacy parameters.

For subjects who were randomized to placebo arm, baseline in Extension Period will be re-defined as last assessment prior to first dose in Extension on Day 1-EX. This will separate the effect of FG-3019 from placebo.

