4.5 General Layout

For subjects who have been treated in extension, all safety and efficacy data, including both the Randomized Treatment Period and Extended Treatment Period, will be summarized descriptively by scheduled visit. All data will be presented in data listings.

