5.6 Summary of the Efficacy Data in the Extension Period

Efficacy parameters, including change from baseline in FVC_{pp}, FVC (L), HRCT fibrosis score, and SGRQ total and domain scores, are summarized descriptively at each scheduled visit for subjects who have been treated in extension.

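### In the extension, Arm A's FVC change is meant to show long-term effect, but it is averaged only over subjects admitted and kept by that same change, so the mean is biased upward

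*SAP*

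**What the plan says.** For Arm A, SAP 3.2.1 states that "efficacy endpoints are defined as change from the original baseline at study entry. These summaries will enable evaluation of long-term effect". SAP 4.3, on the choice of baseline, adds: "This definition will enable evaluation of long term treatment effect in safety and efficacy parameters".

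The population is set elsewhere. Under SAP 5.6 the efficacy parameters (FVC % predicted, FVC in litres, HRCT fibrosis score, SGRQ) "are summarized descriptively at each scheduled visit for subjects who have been treated in extension". SAP 4.5 uses the same subjects, and SAP 4.2 allows no imputation: "All efficacy and safety will be summarized based on available observed data".

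Entry and retention are set in the Protocol and repeated in SAP 2.1:

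- **Amendment 1 or later (4.2.3.2).** The extension is offered to "All subjects in Arm A whose FVC percent predicted value is greater than the original pre-treatment baseline in the Randomized Treatment Period". They "may continue treatment until FVC percent predicted is equal to or less than the pre-treatment baseline on two consecutive scheduled evaluations".
- **Original protocol (4.2.3.1).** The offer goes to Arm A subjects "whose FVC percent predicted value shows less than 3% absolute decrease from baseline in the Randomized Treatment Period will be offered participation". They stop after a fall of 3 points or more from that baseline at two consecutive evaluations.
- **Placebo (4.2.3.3).** All are offered entry with no FVC threshold, and their baseline is reset.

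SAP 4 says that no formal inference will be made. It also mentions summaries for all treated subjects.

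**The concern.** For FVC, the entry variable, the retention variable and the reported endpoint are one quantity: change in FVC % predicted from the original baseline. Averaging it over subjects selected for a high value gives a high average whether or not the drug works. FVC in litres is the same measurement on another scale.

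The general statement in SAP 4 does not repair this. Arm A subjects who do not enter the extension have no scheduled spirometry after Week 48; the final visit in Protocol Appendix 3 is a safety visit. SAP 5.6 also does not separate the two entry rules.

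At stake is interpretation. These are the only Arm A FVC results that SAP Part 2 plans beyond Week 48, and the SAP tells the reader to take them as evidence of long-term effect. In a disease where decline is expected, a mean near or above baseline in the second year would look like sustained benefit.

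**Working it through.** **Inputs (Protocol 10.1).** Mean change to Week 48 of -2.8 points (FG-3019, planned effect) and -7.0 (placebo, used here for an inert drug); SD 7.3; 55 per arm; 10% dropout; two-sided 0.05.

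**The plan's own figure.** The SAP gives no figure for the extension, so the check is on the inputs. A difference of 4.2 with SD 7.3 needs 48 evaluable per arm by the normal formula; 48/0.90 = 53.3, so 54, against 55 planned. With 55 x 0.90 = 49.5, so 49 evaluable, power is 80.5% (noncentral t). The stated 80% reproduces.

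**Step 1: Week 48.** The documents do not say which FVC value decides entry. Protocol 4.4.3 and 7.1 point to Week 48, and that reading is used here. Assuming normality, the mean of subjects above cut-off c is

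mean = mu + 7.3 x phi(a) / (1 - Phi(a)), with a = (c - mu)/7.3.

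| Rule | True mean (mu) | Share admitted | Entrants' mean | Excess |
|---|---|---|---|---|
| c = 0 | -2.8 | 35.1% | +4.92 | 7.72 |
| c = 0 | -7.0 | 16.9% | +3.89 | 10.89 |
| c = -3 | -2.8 | 51.1% | +2.90 | 5.70 |
| c = -3 | -7.0 | 29.2% | +1.59 | 8.59 |

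First row: a = 2.8/7.3 = 0.384, phi/(1 - Phi) = 1.057, and -2.8 + 7.3 x 1.057 = +4.92.

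**Step 2: after Week 48.** The documents give no later trajectory and no within-subject noise, so these are assumptions: linear decline (means of -5.6 and -14.0 at 48-EX without selection), visits every 12 weeks, and stopping after two consecutive values at or below c. Nine structures were simulated with 500,000 subjects each: random slope and random walk, each with measurement SD 2, 3 or 4, and compound symmetry with correlation 0.3, 0.6 or 0.9. Displayed means at 48-EX for c = 0, planned / inert:

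| Structure | 1st setting | 2nd | 3rd |
|---|---|---|---|
| Random slope (SD 2, 3, 4) | 9.6 / 7.3 | 8.3 / 5.7 | 5.9 / 2.6 |
| Random walk (SD 2, 3, 4) | 4.5 / 0.8 | 3.8 / -0.2 | 2.6 / -1.8 |
| Compound symmetry (0.3, 0.6, 0.9) | -1.5 / -7.9 | 1.1 / -4.0 | 2.7 / -1.3 |

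Every entry lies above its unselected mean, by 4.1 to 15.2 points (planned) and 6.1 to 21.3 (inert). The displayed gap between a working and an inert drug is 2.3 to 6.4 points against a true 14.0 - 5.6 = 8.4, that is 27% to 76% of it. For c = -3 the means are -2.6 to +6.4 (planned) and -9.0 to +3.8 (inert), again all too high.

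**Step 3: other readings of the entry value.** If any randomised-period visit, or every visit, decides entry, the 48-EX excess stays positive in all nine structures. For c = 0 it is 3.1 to 14.1 (any visit) and 6.1 to 17.4 (every visit) with the planned effect, and 4.8 to 20.3 and 8.3 to 23.2 if inert. Under the any-visit reading, the inert-drug Week 48 mean for c = 0 is -4.9 to -1.0: above -7.0, but not positive.

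**Step 4: removal under Protocol 8.** Taking out subjects with two consecutive falls of 10 points or more leaves 87-92% completing (planned) and 76-83% (inert). The c = 0 entrants' Week 48 means stay at about +4.9 and +3.9.

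**The case against.** The strongest reply is that the two SAP sentences merely justify a choice of baseline: the original one for Arm A, a reset one for placebo. Neither claims to estimate an effect in all of Arm A. The SAP prints the entry and stopping rules, makes no inference and attaches no decision to these means. Part of this stands: the selection is not hidden, and no error rate is touched. But the SAP does assign the summaries a purpose, and a mean does not lose its bias because no test is run on it.

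Four further points stand and limit the claim:

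- SAP 5.6 also plans HRCT and SGRQ. They come from the same selected subjects but are not the selection variable; no bias was computed for them. SAP 4.3 also covers safety, where the purpose need not change.
- A reader might infer that placebo entrants are unselected on FVC. Protocol 8 removes subjects in either arm for a confirmed fall of 10 points or more, and crossover follows completion of 48 weeks. In Step 4 that takes out about 17-24% of an arm with mean -7.0.
- Stopping needs two consecutive failing evaluations, so some values below the threshold remain in the summary.
- The sizes after Week 48 rest on assumed covariance and linear decline.

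A reader might also infer that no all-treated display exists for the randomised period. SAP Part 1 covers that period and was not available, so the documents do not support that inference. Part 1 could not in any case supply later FVC for subjects never admitted.

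**Conclusion.** The point holds for FVC. As a measure of long-term effect in Arm A, the planned extension mean is biased upward. At Week 48, with entry decided on that value, normality and the inputs of Protocol 10.1, the excess is about 7.7 points (Amendment 1 rule) or 5.7 (3-point rule) with the planned effect, and 10.9 or 8.6 if the drug is inert. After Week 48 the direction was the same in every structure and under every entry reading tried; the size is not determined by the documents.

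A stronger reading is tempting: that an inert drug would still show a positive mean throughout the extension. The documents do not support it. Under the Amendment 1 rule the inert-drug mean was negative in 7 of 9 structures at 24-EX and in 5 of 9 at 48-EX, depending on within-subject noise that the documents do not give. Nor does anything here bear on the primary Week 48 comparison. This is a fault of stated purpose and labelling that should be corrected.

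**What to change.** 1. **SAP 3.2.1 and 4.3.** Limit the long-term-effect wording. Describe Arm A extension FVC means (litres and % predicted) as the course of subjects who qualified for and stayed in extended treatment. Note that HRCT and SGRQ come from the same selected subjects. Leave the safety purpose unchanged.
2. **Footnote.** State that Arm A entry and retention required FVC above the original baseline (or a fall of less than 3 points under the original protocol), and that placebo completers were offered entry without that threshold, although FVC-based removal under Protocol 8 applied to both arms. State which FVC value decided entry.
3. **SAP 5.6.** Show original-protocol and amendment entrants separately, and print the all-treated Arm A mean through Week 48 beside the entrants' mean.
4. **Count at each EX visit.** Give the number of Arm A subjects still in extension and above their own rule's threshold (0 or -3), over all treated main-study Arm A subjects. Exclude substudy subjects, whom SAP 2.1 bars from the extension. Show ineligible, declined and stopped subjects separately, splitting stops by FVC rule or other reason. This extends the no-decline display of Protocol 10.3.4.1 past Week 48.

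The cost is a few table columns, a footnote and two changed passages; no new data are needed. The label becomes less favourable. The count is a composite and cannot by itself establish a drug effect: under the Amendment 1 rule the simulated 48-EX share is 7-29% with the planned effect and 0.4-12% if inert. Within each structure it is at least 2.3 times higher with the planned effect, but the ranges overlap and there is no concurrent control.

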3.2.2 Study Drug Exposure and Treatment Compliance

Duration of year 1 exposure = date of last non-zero dose in year 1 – date of first dose + 1.

Duration of extended treatment exposure = date last non-zero dose in extension – date of first dose in extension + 1.

Duration of entire study treatment exposure = date last non-zero dose in study – date of first dose in study + 1.

Number of infusions is defined as the number of non-zero dose infusions.

Compliance in each treatment year = (# of actual doses administered) / (# of expected doses) * 100, where # of expected doses = (last dosing week) / 3 + 1. All components in the formula are within each treatment year from Day 1 – EX year k to Weeks 45 or EOT in year k.

Overall compliance in entire study = (sum of # of actual doses administered in each treatment year) / (sum of # of expected doses in each treatment year) * 100.

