**Figure 1. Study Schema**

#### 4.2.2 Randomized Treatment Phase

Treatment should begin within 42 days of the first screening visit. Study Drug (FG-3019 [30 mg/kg] or placebo) will be administered by IV infusion every 3 weeks for a total of 16 infusions over 48 weeks.

The schedule of assessments of safety and efficacy are provided in Appendix 1 and Appendix 2. Safety and tolerability will be monitored closely by FibroGen. Cumulative safety experience will be evaluated by FibroGen on a regular basis. Final efficacy assessment is in Week 48. Subjects who do not enter the Extended Treatment Phase will undergo end-of-study (EOS) assessment (Appendix 3) on Week 49 (4 weeks after last dose of study drug).

After all subjects complete Week 48 evaluations or prematurely discontinue the study, data will be cleaned and locked for the primary analysis of efficacy and safety.

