### 7.4 Missed Visits

Every attempt should be made to complete all study visits within window as outlined in the Schedule of Assessments ([Appendix 1](#), [Appendix 2](#), and [Appendix 3](#)).

Scheduled visit dates are determined from the time of the first dose, which is defined as Day 1. Protocol-defined visits conducted outside the  $\pm 3$  day study visit window will be recorded as a protocol deviation unless there is an AE/SAE/intercurrent illness. If a dose is delayed due to an AE/SAE/illness, the next dose should occur as soon as possible when the patient is stable so that

the dosing interval is close to 3 weeks. No subject should receive more than one dose in any 7-day period. Missed doses are not to be made up through undertaking extra visits. If a subject misses more than two infusions in any 18-week period throughout the study, or two sequential infusions, the FibroGen Medical Monitor should be notified. Subjects who miss three sequential doses or more than one instance of two sequential doses will not be allowed to continue in the study and will be terminated early. The reason for missed doses should be documented in the subject's clinical record.

For missed visits without an AE/SAE/intercurrent illness, the subject will be asked to resume the planned visit schedule and return for the next scheduled visit. If the subject is unable to perform PFTs at a scheduled visit the PFT can be performed at the next scheduled visit.

Refer to the case report form (CRF) completion guidelines in the Study Reference Manual for additional information on CRF completion requirements for missed visits.

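### On its natural reading, the SAP's expected-dose count stops at the last dose given, so the final run of missed doses in a treatment year drops out of compliance

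*SAP*

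**What the plan says.** SAP section 3.2.2 gives the yearly measure as "Compliance in each treatment year = (# of actual doses administered) / (# of expected doses) * 100", "where # of expected doses = (last dosing week) / 3 + 1". The sentence after it places all components of the formula "within each treatment year from Day 1 – EX year k to Weeks 45 or EOT in year k". Overall compliance pools the years, as ("sum of # of actual doses administered in each treatment year) / (sum of # of expected doses in each treatment year) * 100"). The same section says "Number of infusions is defined as the number of non-zero dose infusions", and its three exposure durations all run to the last non-zero dose. The term *last dosing week* is not defined in Part 2 of the SAP or in the protocol. Part 1 of the SAP is not among the documents.

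Protocol section 4.2.2 plans dosing "every 3 weeks for a total of 16 infusions over 48 weeks" in the randomized phase. Protocol section 7.4 says that missed doses are not made up by extra visits. It requires the Medical Monitor to be told of two sequential misses, and sets a termination rule: "Subjects who miss three sequential doses or more than one instance of two sequential doses will not be allowed to continue in the study".

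**The concern.** A compliance percentage should show how much of the scheduled dosing a subject received while still on treatment. If the denominator ends at the last infusion given, a missed dose counts or not according to its position. Followed by another dose in the same year, it lowers the score. At the end of the year, or of treatment, it disappears.

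The termination rule in protocol section 7.4 makes this matter. When a subject is terminated for three sequential missed doses, those misses come after the last dose given. The measure would then omit the very misses that led to termination.

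Year-end misses raise a second problem. Each year's expected count is fixed separately and then summed, so two misses at the end of one year are not recovered when the subject resumes in the next.

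At stake is how faithfully the plan would report delivery of the every-3-weeks regimen. No efficacy comparison depends on it.

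**Working it through.** **Inputs.** The formulas come from SAP section 3.2.2, the planned number of infusions from protocol section 4.2.2, and the missed-dose rules from protocol section 7.4. I take a treatment year as Weeks 0, 3, ..., 45, as the SAP's bound implies. Protocol Appendix 2 also marks an infusion at Week 48-EX, which lies outside that bound. The dosing patterns below are illustrations, because the documents do not say how many subjects would show them.

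**Plan's own figure.** For a full year, 45/3 + 1 = 16, which matches the 16 planned infusions. Entering the Week 48 visit would give 48/3 + 1 = 17. The formula is therefore built on an infusion week, not on the final visit.

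**Two denominators.** Let A be the doses given, L the week of the last dose given, and T the last scheduled dosing week before the decision to stop (45 if the subject continues).

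- Natural reading: 100 × A / (L/3 + 1)
- Scheduled doses: 100 × A / (T/3 + 1)

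| Weeks missed | Outcome | A | L | Natural reading | T | Scheduled doses |
|---|---|---|---|---|---|---|
| 24, 27, 30 | terminated | 8 | 21 | 8/8 = 100% | 30 | 8/11 = 72.7% |
| 9, then 24, 27, 30 | terminated | 7 | 21 | 7/8 = 87.5% | 30 | 7/11 = 63.6% |
| 6, 9, then 24, 27 | terminated | 6 | 21 | 6/8 = 75% | 27 | 6/10 = 60% |
| 42, 45 | continues next year | 14 | 39 | 14/14 = 100% | 45 | 14/16 = 87.5% |
| 12, 15 | dosed to Week 45 | 14 | 45 | 14/16 = 87.5% | 45 | 14/16 = 87.5% |

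The last two rows isolate the inconsistency. Both subjects miss two doses of 16, yet the natural reading gives 100% when the misses fall at the end of the year and 87.5% when they fall in the middle.

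**General case for three trailing misses.** With k consecutive doses given and the next three missed, L = 3(k − 1), so the expected count is k and the score is always 100%. Against scheduled doses the score is k/(k + 3): 25.0% for k = 1, 62.5% for k = 5, 76.9% for k = 10 and 81.3% for k = 13.

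**Overall compliance.** Suppose Weeks 42 and 45 are missed in one year and all 16 doses are given in the next. The natural reading gives (14 + 16)/(14 + 16) = 30/30 = 100%. Scheduled doses give 30/(16 + 16) = 30/32 = 93.75%.

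**Direction.** L is never later than T, so the natural reading can raise the percentage or leave it unchanged, but cannot lower it.

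**Second reading.** Suppose the bound "Day 1 – EX year k to Weeks 45 or EOT in year k" is taken to define the last dosing week, so that the count runs to the last scheduled dosing week before that limit. If end of treatment falls after Week 30 and before Week 33, the first row becomes 8/(30/3 + 1) = 8/11 = 72.7%. The fourth row becomes 14/(45/3 + 1) = 14/16 = 87.5%.

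**The case against.** The strongest objection is that the inflating reading is not established. Where section 3.2.2 plainly means a dose actually given, it says last non-zero dose. Here it uses a different phrase and then bounds the components by Week 45 or end of treatment. Part 2 also leaves out definitions already given in Part 1, which may define the term. This stands in part: the documents do not settle the meaning. The formula is nevertheless printed in full in Part 2, and its ordinary sense is the week of the last dose. An undefined term that lets two programmers report 100% or 73% from the same records still needs defining.

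A reader might go further and infer any of three stronger claims, which the documents do not support:

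- *Missed doses never count.* Only the final run of misses in a year is lost. Weeks 12 and 15 missed with later dosing are fully counted.
- *Anyone terminated for missed doses scores 100%.* That needs three trailing misses and no earlier miss. One earlier miss gives 87.5%. Termination by two pairs gives 75%, because the first pair stays in the denominator.
- *The formula is an arithmetic error.* It reproduces the planned 16 infusions exactly. The fault is in the definition.

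It is also fair to say that little depends on the result. SAP section 4 plans no formal inference. The text of SAP section 5.5 names duration, number of doses and dose amount, and compliance appears only in its heading. Discontinuations and their reasons are summarized separately under SAP section 5.1. All of this stands and limits the point to a minor one. It does not explain why equal numbers of missed doses should score differently by position.

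**Conclusion.** The point holds as a minor fault of definition. If the last dosing week is the week of the last dose given, compliance omits the final run of missed doses in each treatment year and is biased upward or unchanged. In the examples the overstatement is 27 percentage points for termination after Week 21 with no earlier miss (100% against 73%), 15 points for termination by two pairs of misses (75% against 60%), and 12.5 points for two year-end misses in a subject who continues.

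This rests on the natural reading of an undefined term, on 16 scheduled doses per treatment year, and on hypothetical dosing patterns. The effect on the reported summary cannot be sized, because the number of such subjects is not given. Under the second reading the problem does not arise, but the SAP does not say which reading applies. No endpoint, analysis population or test in Part 2 of the SAP depends on the measure.

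**What to change.** In SAP section 3.2.2, replace the expected-dose formula with: *expected doses = number of scheduled dosing visits (Weeks 0, 3, ..., 45) in treatment year k before the date of the decision to discontinue treatment, not counting the end-of-treatment visit itself, or through Week 45 if the subject continues past that year*. Sum these counts for overall compliance. State also that the missed doses that trigger termination precede the decision and are counted.

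The exclusion of the end-of-treatment visit is needed. Protocol Appendix 3 places that evaluation preferably 3 weeks after the last dose (for subjects with more than four doses), which is the next dosing week. Counting every visit up to and including that date would give a subject dosed through Week 21 and then stopped for another reason 8/9 = 89%, although no dose was missed before the decision.

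The cost is one line of text and a small programming change. Exposure and disposition records are already among the datasets in the SAP appendix. The programmer should confirm that the disposition date used is the decision date and not the visit date. Reported compliance would become slightly less favourable.
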